14.3 Vital Signs

Vital signs will be collected throughout the study; height will be measured at Baseline and Week 40/EOT; weight will be measured at Baseline, Week 2, Week 12, Week 26 and Week 40/EOT. Observed vital signs including weight and BMI and the changes from Baseline at each post-Baseline visit will be summarized using descriptive statistics.

Vital sign values will be considered PCI if they meet the criteria listed in [Table 7](#). The number and percentage of subjects with post-Baseline vital signs that are PCI will be summarized at each post-Baseline visit and for overall post-Baseline. For the overall post-Baseline summaries, all post-Baseline values will be considered, including unscheduled and out of window values. Subjects with multiple PCI values for a given parameter will be counted only once for that parameter. For the by-visit summary, the numerator for the percentage is the number of subjects

with a post-Baseline PCI vital sign for the given parameter and visit, and the denominator is the number of subjects with non-missing values for the given parameter and visit. For the overall post-Baseline summary, the numerator for the percentage is the number of subjects with at least 1 post-Baseline PCI vital sign for the given parameter, and the denominator is the number of subjects with at least 1 post-Baseline vital sign for the given parameter. A listing of overall and of subjects with any PCI vital sign values will be provided.

Table 7 Criteria for Potentially Clinically Important Vital Signs

| Vital Sign Parameter | Unit | Criteria | | | |
|--|------|----------------|--------|-----------------------------|--------------------------------|
| | | Observed Value | And/Or | Change Relative to Baseline | Change from Supine to Standing |
| Systolic blood pressure (supine or sitting) | mmHg | ≥180 | And | Increase of ≥20 | - |
| | | ≤90 | And | Decrease of ≥20 | - |
| Diastolic blood pressure (supine or sitting) | mmHg | ≥105 | And | Increase of ≥15 | - |
| | | ≤50 | And | Decrease of ≥15 | - |
| Pulse (supine or sitting) | bpm | ≥120 | And | Increase of ≥15 | - |
| | | ≤50 | And | Decrease of ≥15 | - |
| Weight | kg | Not Applicable | | Increase of ≥7% | - |
| | | | | Decrease of ≥7% | - |

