1. INTRODUCTION

This statistical analysis plan (SAP) provides a technical and detailed elaboration of the statistical analyses of efficacy and safety data as described in the protocol amendment 2, dated 07 August 2020.

Specifications for tables, figures, and listings are contained in a separate document. Statistical analyses for population pharmacokinetic (PK) and PK/pharmacodynamics (PD) modeling will be presented in a separate report and therefore will not be included in this SAP.

This plan should be read in conjunction with the study protocol and the electronic case report forms (eCRFs).

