5.1 General Data Reporting Conventions

Continuous variables will be summarized using the following descriptive statistics: number of subjects, mean, standard error (SE), standard deviation (SD), median, minimum, and maximum. For descriptive summaries of efficacy, the 95% confidence interval (CI), calculated as $\text{mean} \pm 1.96 * \text{SE}$, will be presented. Unless specified otherwise, means, medians, and CIs will be presented to one more decimal place than the raw data, and the SDs and SEs will be presented to two more decimal places than the raw data. In general, the maximum number of decimal places is 4 and values will be truncated to 4 decimal places in situations where there are more than 4 decimal places. Wherever possible data will be decimal aligned.

Height, weight and BMI will be presented with a maximum of one decimal place.

Categorical variables will be summarized by the number of subjects and the percentage of subjects in each category; the number of subjects and the percentage of subjects with missing data will be summarized for demographic and baseline characteristics (if applicable). Categories with zero counts will not have zero percentages displayed. For demographic summaries, percentages will be calculated by using the total number of subjects in the given treatment group of the antecedent study as the denominator. Percentages will be presented with one decimal place.

Duration in months will be calculated as ([the number of days / 365.25] *12).

Lab values, not including PK concentration data, that are collected with “<” or “>” signs will generally be analyzed as the numerical value without the sign in tables and figures. In listings, these data will be reported as collected with the sign.

For each continuous measure in safety and efficacy analyses, change from baseline results will be presented by treatment group of the antecedent study and overall in two ways:

1. Main analysis: using the baseline of this study, as defined in [Section 5.5](#), to report the changes across the timepoints of this open-label Study ACP-2566-004.
2. Exploratory analysis: using the baseline from the antecedent study, ACP-2566-003, to report the changes across the timepoints of this open-label Study ACP-2566-004.

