5.4 Baseline Definition

Data from the latest predose value of (Study ACP-2566-003 Week 12/EOT visit, unscheduled visit within Week 12 window, visit within 2 weeks of last double-blind dose, or Study ACP-2566-004 Baseline Visit) will be carried over as Baseline information in the present study, as applicable (e.g., not for the CGI-I for which this is not applicable).

Subjects for whom the Baseline visit of this study is not on the same day as the Week 12/EOT visit of the antecedent study (e.g., subjects in the antecedent study who were prevented from entering this study by the COVID-19 public health emergency) will have blood drawn for Baseline values three to fourteen days before the Baseline visit.

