8. DEMOGRAPHICS AND BASELINE CHARACTERISTICS

Demographics and baseline characteristics will be summarized for the Safety Analysis Set using descriptive statistics. Variables include, but are not limited to, age, age group (5-10 years old, 11-15 years old, and 16-20 years old), race, ethnicity, height, weight, BMI, Baseline RSBQ total score, Baseline RSBQ severity (< 35 total score and \geq 35 total score), and Baseline CGI-S score.

Race will also be categorized by White vs. Non-White. The reported age reflects a subject's age at the informed consent date. Baseline characteristics for subjects in ACP-2566-004 will also be summarized using the baseline of the antecedent study separately.

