14. SAFETY ANALYSES

All safety analyses will be performed using the Safety Analysis Set. Safety summaries will be summarized using descriptive statistics by treatment group of the antecedent study and overall. For each continuous measure in clinical laboratory variables, vital signs, and electrocardiogram, change from baseline results will be presented in two ways as specified in [Section 5.1](#).

The primary safety endpoints are:

- Treatment-emergent adverse events (TEAEs)
- Serious adverse events (SAEs)
- Withdrawals due to adverse events (AEs)
- Potentially clinically important changes in other safety assessments

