14.4 Electrocardiogram (ECG)

12-lead ECGs are collected throughout the study at every visit.

When ECG is collected multiple times (e.g. at Screening visit, Baseline visit both before dosing and 2-3 hours after dosing, and Week 40/EOT/ET visit), the average of all available values on the same day will be considered as one assessment for the summaries, except for Day 1 where averages will be by pre-dose and post-dose averages. The averages will be rounded to integer values.

Observed (average) values of ECG variables (e.g., heart rate, PR interval, QRS interval, QT interval, QTcB and QTcF interval) and the changes from Baseline at each assessment time point will be summarized by treatment group.

Observed (average) values of QTcB and QTcF will also be categorized into the following categories (msec) and the number and percentage of subjects in each category will be summarized by treatment group at each visit and for the overall post-Baseline maximum:

- Observed: ≤450, 451 - ≤480, 481 - ≤500, and >500; >450; >480.

- Change from Baseline: ≤ 10 , $11 - 30$, $31 - 60$, and > 60 ; > 30 .

For cardiologist's interpretations, the number and percentage of subjects with ECG results that are determined as normal or abnormal will be summarized at scheduled visits. The overall post-baseline worst interpretation will also be summarized (i.e. if a subject has one or more post-baseline ECG results that is/are considered as abnormal, this subject will be counted in the abnormal category). Cardiologist's interpretations will also be summarized in a shift table. The shifts from Baseline to overall post-Baseline worst interpretation will also be presented. For the by-visit shift summary, the denominator is the number of subjects with non-missing cardiologist's interpretation at Baseline and the given visit for the given treatment group. For the summaries of shift from Baseline to the overall post-Baseline worst interpretation, the denominator is the number of subjects with non-missing Baseline and at least 1 post-Baseline cardiologist's interpretation for the given treatment group.

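### Must the weight ±7% counts and the QTc-change categories also be given from the Study 003 baseline?

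*SAP*

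**What the plan says.** SAP 14 opens with a rule for all its subsections: "For each continuous measure in clinical laboratory variables, vital signs, and electrocardiogram, change from baseline results will be presented in two ways". It refers back to SAP 5.1, where the main analysis uses this study's Baseline and the exploratory one works by "using the baseline from the antecedent study, ACP-2566-003, to report the changes across the timepoints of this open-label Study". Safety tables are split by antecedent arm, with an overall column.

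SAP 5.4 defines Baseline as "Data from the latest predose value of (Study ACP-2566-003 Week 12/EOT visit, unscheduled visit within Week 12 window" and so on, down to this study's own Baseline visit. This agrees with Protocol 9.5.1, which carries the Week 12/EOT data forward except for subjects delayed by COVID-19. Protocol 5.1.3.1 expects that, in most cases, the last Study 003 dose was taken on the morning of that visit.

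SAP 14.3 then says: "The number and percentage of subjects with post-Baseline vital signs that are PCI will be summarized at each post-Baseline visit". In Table 7, blood pressure and pulse need both an absolute value and a change, whereas weight needs only a change of 7% or more in either direction. For the QTc categories, including change from Baseline, SAP 14.4 says "the number and percentage of subjects in each category will be summarized by treatment group at each visit and for the overall post-Baseline maximum". Table 8 adds a change of more than 60 msec for QTcB and QTcF. Neither subsection mentions the Study 003 baseline.

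SAP 8, by contrast, says "Baseline characteristics for subjects in ACP-2566-004 will also be summarized using the baseline of the antecedent study separately". SAP 1 notes: "Specifications for tables, figures, and listings are contained in a separate document".

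**The concern.** Potentially important changes in weight, other vital signs and ECG belong to a primary endpoint (Protocol 2.1.1). A former-placebo subject's Baseline is drug-free. A former-trofinetide subject's Baseline, on direct rollover, comes after about 12 weeks of drug. The same flag therefore measures change since before drug in one column and change since Week 12 of drug in the other.

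Weight is the main case because no absolute threshold backs it up. Protocol 1.3 reports diarrhea in 56% of subjects at 200 mg/kg BID against 4% on placebo in the pediatric Phase 2 study, so cumulative weight loss is a fair safety question. If the two-baseline rule stops at means and medians, nobody would tabulate how many of the longest-exposed subjects crossed 7% over both studies.

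**Working it through.** **1. What depends on the baseline.** Laboratory and urinalysis criteria (Tables 5 and 6), QRS, PR and observed QTc use no change from baseline. Blood pressure and pulse depend on it only in part. Weight and the QTc-change items depend on it fully. Protocol 1.3 reports no treatment-attributable QTc change in the two Phase 2 Rett studies, so the documents give no reason to expect a QTc effect. That leaves weight.

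**2. Arithmetic of the 7% rule.** Cumulative change = (1 + change in 003) × (1 + change here) − 1.

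- Two losses of 5%: 0.95 × 0.95 − 1 = −9.75%, with no flag from the open-label Baseline.
- Limit for two steps each under 7%: 0.93 × 0.93 − 1 = −13.5%.
- After a loss of 2%, 3% or 5% in Study 003, the flag comes at a cumulative loss of 1 − 0.98 × 0.93 = 8.9%, 1 − 0.97 × 0.93 = 9.8%, or 1 − 0.95 × 0.93 = 11.7%.

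The mechanism is real. How many subjects it touches is a separate question.

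**3. Illustrative counts.** The documents give no weight effect, no variability and no allocation ratio, so every input here is assumed: 90 former-trofinetide subjects (half of the ceiling of 180 in SAP 3.5); independent normal changes with SD 4% in Study 003 and 5% over 40 weeks here; growth of either 6% a year (6 × 40/52 = +4.6% over 40 weeks) or zero. Expected numbers with a loss of 7% or more at Week 40, from 4,000,000 draws:

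| Open-label growth | Mean change in 003 | From open-label Baseline | From 003 baseline |
|---|---|---|---|
| +4.6% | −4% / −2% / 0 | 1 | 11 / 6 / 3 |
| 0 | −4% / −2% / 0 | 7 | 29 / 19 / 12 |
| 0 | +2% | 7 | 7 |

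At zero mean change in Study 003 the gap is added variance only and would arise on placebo too.

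**4. What the gap consists of.** In the growth case at −4%, 7.2 of the 10.9 expected subjects had already lost 7% or more by the end of Study 003, and about 3.1 crossed in two steps each below 7%. At −2% the split is 3.0 and 2.4 of 6.1. Without growth at −4%, it is 13.9 and 9.9 of 28.8. The remainder in each case lost 7% or more within this study and are flagged from either baseline. Much of the gap is thus weight lost before the first open-label dose.

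**5. Sensitivity to the assumed SD.** Scaling the 40-week SD to 12 weeks gives 5 × √(12/40) = 2.74%, not 4%. The growth row then becomes about 8 / 4 / 2 and the no-growth row about 27 / 17 / 10.

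**6. What the repeat counts would carry with them.** The SAP 8 age bands are "age group (5-10 years old, 11-15 years old, and 16-20 years old", so many subjects are growing. With 6% a year and an SD of 5% at 40 weeks, P(gain ≥ 7%) = 1 − Φ((7 − 6t/52) / (5√(t/40))). This is 0.317 at t = 40 weeks and 0.430 at 52. For a COVID-19 re-entrant at the 12-month limit (12 + 52 + 40 = 104 weeks) it is 0.732. Elapsed time from the Study 003 baseline is about 14, 24, 38 and 52 weeks at Weeks 2, 12, 26 and 40 for direct rollovers. The arms would still differ in time on drug, about 52 weeks against 40 at the end.

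**7. Reading the texts together.** The rule opening SAP 14 turns on the measure being continuous and names vital signs and ECG. Weight and QTc are continuous, and Tables 7 and 8 and the QTc categories label the disputed items as changes from baseline. An analyst can apply the rule to them without departing from the text. SAP 8 needed its own sentence because baseline characteristics are not change results. SAP 5.1 cites Section 5.5 for the Baseline definition, which is in 5.4; this is a clerical slip, since 5.5 holds the visit windows.

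**The case for a change.** The strongest contrary case is textual. SAP 5.1 treats continuous and categorical variables in separate paragraphs and ties the two-baseline rule to continuous measures. Counts of subjects over a threshold are categorical. Sections 14.3 and 14.4 specify numerators, denominators and unscheduled values in detail yet never mention the antecedent baseline. Two programmers could produce different tables. Means from the Study 003 baseline cannot show how many subjects crossed 7%, and a listing is a poor substitute for a count. The repeat would be cheap, because the SAP already uses that baseline.

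What stands: the wording is ambiguous, and whether the repeat counts are planned cannot be settled without the table specifications. What does not stand is that the primary endpoint suffers. Protocol 9.5.2 asks for changes from Baseline, Protocol 9.5.1 fixes which Baseline that is, and neither asks for a Study 003 display. The ambiguity concerns how far an exploratory addition reaches.

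**Conclusion.** No change to the plan is needed. Followed as written, the counts are valid from the Baseline the protocol sets. Continuous weight and QTc change from the Study 003 baseline is promised as well, all collected data are listed, and no hypothesis is tested. The open question is a detail of a supplementary table, which the table specifications can settle and which a sensible reading of SAP 14 already answers.

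The effect on weight-loss counts could be nil or appreciable: from 7 against 7 to 7 against 29 of 90 in the cases above. Those figures rest wholly on assumed means, SDs, growth and arm size, and part of each gap is loss completed in Study 003. No effect is claimed for QTc, blood pressure or pulse. A team that chooses to show weight counts from the Study 003 baseline should note the varying elapsed time, mark the COVID-19 re-entrants and read the gain counts with growth in mind. That is an option for reporting, not a correction.

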14.4 Electrocardiogram (ECG)

12-lead ECGs are collected throughout the study at every visit.

When ECG is collected multiple times (e.g. at Screening visit, Baseline visit both before dosing and 2-3 hours after dosing, and Week 40/EOT/ET visit), the average of all available values on the same day will be considered as one assessment for the summaries, except for Day 1 where averages will be by pre-dose and post-dose averages. The averages will be rounded to integer values.

Observed (average) values of ECG variables (e.g., heart rate, PR interval, QRS interval, QT interval, QTcB and QTcF interval) and the changes from Baseline at each assessment time point will be summarized by treatment group.

Observed (average) values of QTcB and QTcF will also be categorized into the following categories (msec) and the number and percentage of subjects in each category will be summarized by treatment group at each visit and for the overall post-Baseline maximum:

- Observed: ≤450, 451 - ≤480, 481 - ≤500, and >500; >450; >480.

- Change from Baseline: ≤ 10 , $11 - 30$, $31 - 60$, and > 60 ; > 30 .

For cardiologist's interpretations, the number and percentage of subjects with ECG results that are determined as normal or abnormal will be summarized at scheduled visits. The overall post-baseline worst interpretation will also be summarized (i.e. if a subject has one or more post-baseline ECG results that is/are considered as abnormal, this subject will be counted in the abnormal category). Cardiologist's interpretations will also be summarized in a shift table. The shifts from Baseline to overall post-Baseline worst interpretation will also be presented. For the by-visit shift summary, the denominator is the number of subjects with non-missing cardiologist's interpretation at Baseline and the given visit for the given treatment group. For the summaries of shift from Baseline to the overall post-Baseline worst interpretation, the denominator is the number of subjects with non-missing Baseline and at least 1 post-Baseline cardiologist's interpretation for the given treatment group.

Electrocardiogram variable average values will be considered PCI if they meet the criteria listed in Table 8. The number and percentage of subjects with post-baseline PCI values will be summarized by treatment group at each post-Baseline visit and for overall post-Baseline. For the by-visit summary, the numerator for the percentage is the number of subjects with a post-Baseline PCI ECG for the given parameter, visit and treatment group, and the denominator is the number of subjects with non-missing values for the given parameter, visit and treatment group. For the overall post-Baseline summary, the numerator for the percentage is the number of subjects with at least 1 post-Baseline PCI ECG for the given parameter and treatment group, and the denominator is the number of subjects with at least 1 post-Baseline ECG value for the given parameter and treatment group. A listing of overall and of all subjects with any PCI ECG values will be provided.

Table 8 Criteria for Potentially Clinically Important ECG Values

| ECG Parameter | Unit | High PCI Criteria |
|----------------------------|------|-------------------|
| QRS Interval | msec | ≥ 120 |
| PR Interval | msec | ≥ 220 |
| QTcB | msec | > 500 |
| QTcF | msec | > 500 |
| QTcB: change from baseline | | > 60 msec |
| QTcF: change from baseline | | > 60 msec |

14.5 Physical Examination

Physical examinations are performed throughout the study at every visit in the clinic. Physical examination results (normal, abnormal, and not done) will be summarized in a frequency table by body system and visit. A listing of physical examination data will be listed.

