Seizures are common, although not diagnostic. Commonly observed symptoms include awake breathing disruptions, scoliosis, and interest in social interaction (intense eye communication) (Neul et al. 2010; Percy et al. 2010). Gastrointestinal symptoms, including constipation and chewing and swallowing difficulties, are observed in the majority of patients with RTT (Motil et al. 2012). Sudden changes in mood, screaming and inconsolable crying are common behaviors in children and adolescents with RTT (Mount et al. 2001, 2002; Robertson et al. 2006; Cianfaglione et al. 2015). These impairments can further exacerbate

other symptoms and disrupt activities of daily living including educational, recreational and treatment opportunities (Epstein et al. 2016; Perry et al. 1991; Thompson and Iwata 2001; Lemmi et al. 2016). Autonomic manifestations, which include abnormalities in cardiac and respiratory function, as well as in peripheral circulation, are considered to be predominantly of central nervous system origin. Rett syndrome is also characterized by impaired growth affecting the brain and other organ systems.

Loss of purposeful hand use is a defining aspect of RTT during the onset of regression and at least 30% of individuals remain without any type of purposeful hand use (Downs et al. 2010). Individuals with some purposeful hand movements vary in their level of ability to reach for and grasp objects. The ability to self-feed is observed in 25-43% (Cass et al. 2003; Larsson et al. 2005; Downs et al. 2011). Poorer levels of hand function are associated with both age and severity of mobility impairment (Downs et al. 2011).

In adulthood, a late motor deterioration stage occurs, characterized by worsening dystonia, rigidity, and in some cases deterioration in the ability to walk and parkinsonian symptoms. Affected individuals have a yearly death rate between 1% and 2%, with 25% of all deaths characterized as sudden and unexpected (Kerr et al. 1997; Samaco and Neul 2011). Women with RTT can survive into their fifties and occasionally longer (Samaco and Neul 2011).

There are no medicines approved for the treatment of RTT. Treatment focuses on the management of each patient's symptoms and, even in that regard, is often unsatisfactory and has only a limited effect on functional improvement. Accordingly, the burden on families and other caregivers is very great (Palacios-Ceña et al. 2018).

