6.2 Safety Assessments

6.2.1 Physical Examination

A general physical examination will be conducted at Baseline and at all other designated visits. When a study visit takes place off-site, the physical examination will not be required. The physical exam procedures will include the following organ systems:

- Neurological
- Head, ears, eyes, nose, and throat
- Skin
- Cardiovascular
- Respiratory
- Abdomen
- Genitourinary (optional)
- Musculoskeletal

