- Urinalysis tests include the following:
 - Blood, RBCs, WBCs, protein, glucose, ketones, specific gravity, pH

Clinical laboratory values (in Système International [SI] units) and the change from Baseline values will be summarized at each post-Baseline visit using descriptive statistics. The overall minimum, maximum as well as the last post-Baseline observed and change from Baseline values will also be summarized. For urinalysis with categorical results, the number and percentage of subjects will be tabulated by category at Baseline and each post-Baseline visit, and the denominator is the number of subjects with non-missing values for the given parameter and visit.

Laboratory values will also be summarized in shift tables to determine the number and percentage of subjects with values classified as below, within, and above normal ranges at each post-Baseline visit relative to the same classification at the Baseline visit. For the by-visit shift summary, the denominator is the number of subjects with non-missing values at Baseline and the given visit for the given parameter. For the shift to the overall post-Baseline minimum or

maximum, all post-Baseline values will be considered, including unscheduled and out of window values and the denominator is the number of subjects with non-missing Baseline value and at least 1 post-Baseline value for the given parameter.

Clinical laboratory values are potentially clinically important (PCI) if they meet either the low or high PCI criteria listed in [Tables 5](#) and [6](#). The number and percentage of subjects with post-Baseline PCI values for each of the categories in Table 5 and 6 will be summarized for selected parameters. For the overall post-Baseline summaries of PCI values, all post-Baseline values will be considered, including unscheduled and out of window values. Subjects with multiple PCI values for a given parameter will be counted only once for that parameter. For the overall post-Baseline summary, the numerator of the percentage is the number of subjects with at least 1 post-Baseline PCI laboratory value for the given parameter, and the denominator is the number of subjects with at least 1 post-Baseline laboratory value for the given parameter.

Table 5 Criteria for Potentially Clinically Important Laboratory Values – Hematology and Chemistry

| Analyte | Conventional Unit | Low PCI Criteria | High PCI Criteria | SI Unit | Low PCI Criteria | High PCI Criteria |

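### SAP 14.5 tabulates physical examination results by visit without pairing them to Baseline, so the table does not give the number of subjects who became abnormal

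*SAP*

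**What the plan says.** SAP 14.5 plans two outputs for the physical examination. The first is a table: "Physical examination results (normal, abnormal, and not done) will be summarized in a frequency table by body system and visit". The second is a listing: "A listing of physical examination data will be listed". The section names no shift from Baseline, no worst post-Baseline category and no count of newly abnormal subjects. It also states no denominator.

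The general change-from-Baseline rule in SAP 14 does not reach the examination: "For each continuous measure in clinical laboratory variables, vital signs, and electrocardiogram, change from baseline results will be presented in two ways". SAP 5.1 is likewise limited to continuous measures.

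Other safety assessments are compared within subject. SAP 14.2 says "Laboratory values will also be summarized in shift tables". SAP 14.4 cross-tabulates the cardiologist's normal/abnormal ECG interpretation against Baseline, by visit and for the worst post-Baseline result. SAP 14.3 gives vital signs changes from Baseline and criteria for potentially clinically important values.

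On data collection, Protocol 6.2.1 says "A general physical examination will be conducted at Baseline and at all other designated visits", and adds: "When a study visit takes place off-site, the physical examination will not be required".

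**The concern.** A by-visit share of abnormal findings is a prevalence. It answers the question of change only if few subjects are abnormal at the start and much the same subjects are examined each time. Neither can be assumed here.

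On the first condition, Protocol 1.1 says of Rett syndrome: "Commonly observed symptoms include awake breathing disruptions, scoliosis". It also describes frequent gastrointestinal symptoms and late motor deterioration. These bear on systems examined under Protocol 6.2.1 (neurological, respiratory, abdomen, musculoskeletal), so a good many subjects are likely to be abnormal in some system before the first open-label dose. On the second, an off-site visit may have no examination, and some subjects will leave before Week 40.

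A flat or falling abnormal share could then be read as reassuring when new findings are offset by resolved ones, or when abnormal subjects are no longer being examined. A rising count could equally reflect more examinations and no change in anyone.

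**Working it through.** The plan has no figure of its own to reproduce: the study is descriptive and its size is not based on power (Protocol 9.2 and 9.3). The check compares the text of the sections and then illustrates what the planned table leaves open.

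**Side by side**

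| Assessment | Scale | Within-subject summary in the SAP |
|---|---|---|
| Laboratory (14.2) | continuous, and low/normal/high | change from Baseline, shift tables |
| Vital signs (14.3) | continuous | change from Baseline, criteria relative to Baseline |
| ECG interpretation (14.4) | normal/abnormal | shift by visit and to worst, paired denominators |
| Physical examination (14.5) | normal/abnormal/not done | none; by-visit table and listing |

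The ECG interpretation is the closest comparator because the scale is the same.

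**Inputs.** N = 180 is the approximate maximum enrolment in Protocol 9.3. The abnormality and attendance rates below are assumptions, since the documents give none.

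**1. Everyone examined at both times.** Let A0 be the number abnormal in one body system at Baseline and A1 the number abnormal later. The number newly abnormal lies between max(0, A1 − A0) and min(N − A0, A1). With the count unchanged (A1 = A0):

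| Assumed Baseline rate | A0 = A1 | Newly abnormal |
|---|---|---|
| 30% | 54 | 0 to min(126, 54) = 54 |
| 50% | 90 | 0 to min(90, 90) = 90 |
| 70% | 126 | 0 to min(54, 126) = 54 |
| 90% | 162 | 0 to min(18, 162) = 18 |

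A net rise does set a lower bound. At 70%, a later count of 136 means at least 136 − 126 = 10 newly abnormal, and at most 54.

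**2. Not everyone examined at Baseline.** Suppose 36 of the 180 have no Baseline examination, all 180 are examined later, the rate is 70% throughout and nobody changes. The abnormal count goes from 0.70 × 144 ≈ 101 to 0.70 × 180 = 126, a rise of 25 with no new finding. The lower bound in step 1 no longer holds.

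**3. Abnormal subjects less often examined at Week 40.** Suppose 30% are abnormal at Baseline, nobody changes, and 50% of abnormal and 30% of normal subjects are not examined at Week 40, through dropout or an off-site visit. The share among those examined becomes (0.30 × 0.50) / (0.30 × 0.50 + 0.70 × 0.70) = 0.15 / 0.64 = 23.4%, down from 30%. A paired table on the same data would show no newly abnormal subjects among those normal at Baseline and re-examined (0.49 × 180 ≈ 88).

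**The case against.** The strongest reply is that the safety information is already covered. Protocol 7.1.1 counts any unfavourable, unintended sign as an adverse event and excludes a stable chronic condition only while it does not worsen. Protocol 7.2.2.1 lets sustained worsening define an onset. SAP 14.1 restricts treatment-emergent events to those starting after the first dose and sets aside Day 1 events that rest on pre-dose findings. That route separates new from pre-existing findings, and it picks up worsening within 'abnormal', which a normal/abnormal shift table cannot. The listing holds each subject's sequence. This stands, and it is why the point is minor. Adverse event reporting does depend on the investigator judging a finding reportable, so a systematic tabulation remains a useful cross-check.

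A reader might infer that the table offers no comparison with Baseline, or can never show a new abnormality. The documents do not support that. The examination is done at Baseline and the table is by visit, so Baseline is presumably one of its columns, and with complete examinations a net rise would prove some new findings. 'Not done' is a displayed category, so missing examinations are visible.

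A reader might also infer that a primary endpoint is left unanalysed, because one of them is "Potentially clinically important changes in other safety assessments". The examination is a safety assessment under Protocol 6.2, but the SAP sets potentially clinically important criteria only for laboratory values, vital signs and ECG, and Protocol 9.5.2 does not name the examination among the primary analyses. The SAP does not promise an analysis of change here and then omit it.

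Finally, the upper ends of the ranges are extreme. At 30%, 54 newly abnormal subjects would require all 54 who were abnormal at Baseline to become normal, which is implausible for a finding such as scoliosis. Table specifications are in a separate document (SAP 1) and might include a shift table, though the SAP text does not call for one.

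**Conclusion.** The point holds as a minor weakness of presentation. As written, SAP 14.5 describes how common abnormal findings are at each visit among whoever was examined. It does not report how many subjects moved from normal to abnormal, although Baseline and later examinations are both collected and the SAP already does this for the ECG interpretation.

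No size can be stated from the documents. The ranges above rest on assumed Baseline rates of 30% to 90% and assumed patterns of missing examinations. They show what the table leaves undetermined and do not estimate how many new findings will occur. The conclusion itself needs only that some subjects are abnormal at Baseline and that the examined set differs between visits. The protocol's disease description makes the first likely, and its off-site rule allows the second.

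**What to change.** Supplement the frequency table in SAP 14.5 with a shift table by body system: Baseline normal or abnormal against each post-Baseline visit and against the worst post-Baseline result. Adopt the SAP 14.4 denominators: subjects with a result at both Baseline and the given visit or, for the worst result, at Baseline and at least one later examination. Exclude 'not done'. Present it by antecedent treatment group and overall, as SAP 14 already does for safety summaries, and report the percentage newly abnormal among those normal at Baseline.

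The cost is a wording change and one more table in a format already specified for ECG; no new data or visits are needed. Denominators will be small where most subjects are abnormal at Baseline (18 of 180 at an assumed 90%) or where visits were off-site. The table will not show worsening within 'abnormal', which stays with adverse event reporting. For subjects already on trofinetide in the antecedent study, it shows change during the extension only.
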